5.4.3.4 Congenital Anomalies/Birth Defects

Any congenital anomaly/birth defect in a child born to a female patient exposed to GDC-8264 or the female partner of a male patient exposed to GDC-8264 should be classified as a serious adverse event, recorded on the adverse event eCRF, and reported to the Sponsor immediately (i.e., no more than 24 hours after learning of the event; see Section 5.4.2).

5.5 FOLLOW-UP OF PATIENTS AFTER ADVERSE EVENTS

5.5.1 Investigator Follow-Up

The investigator should follow each adverse event until the event has resolved to baseline grade or better, the event is assessed as stable by the investigator, the patient is lost to follow-up, or the patient withdraws consent. Every effort should be made to follow all serious adverse events considered to be related to study treatment or trial-related procedures until a final outcome can be reported.

During the adverse event reporting period (defined in Section 5.3.1), resolution of adverse events (with dates) should be documented on the adverse event eCRF and in the patient's medical record to facilitate source data verification.

All pregnancies reported during the study should be followed until pregnancy outcome, with follow-up information on the infant collected according to procedures outlined in Section 5.4.3.

5.5.2 Sponsor Follow-Up

For serious adverse events, adverse events of special interest, and pregnancies, the Sponsor or a designee may follow up by telephone, fax, email, and/or a monitoring visit to obtain additional case details and outcome information (e.g., from hospital discharge

GDC-8264—Genentech, Inc. 89/Protocol GA43861, Version 4 summaries, consultant reports, autopsy reports) in order to perform an independent medical assessment of the reported case.

6. STATISTICAL CONSIDERATIONS AND ANALYSIS PLAN

The primary analyses of safety, PK, and efficacy data will be performed after all enrolled patients have either completed the **status** visit or have discontinued from the study prior to **status** and all data from this period are in the database and have been cleaned and verified. The final analyses of complete data for the study will be performed when all

enrolled patients have either completed the **study** study period or discontinued early from the study, all data from the study are in the database, and the database is locked.

Detailed specifications of the statistical methods will be described in the Data Analysis Plan (DAP).

6.1 DETERMINATION OF SAMPLE SIZE

This study is exploratory in nature. The overall purpose of the study is to identify an optimal dose for GDC-8264 for future studies, using all available safety, PK, and efficacy data. A sample size of approximately 20 patients per dose cohort is believed to be clinically appropriate to assess the preliminary safety, pharmacokinetics, and efficacy in this initial study in patients with aGVHD and to inform future development of GDC-8264. The sample size calculation is not based on a statistical power consideration.

6.2 SUMMARIES OF CONDUCT OF STUDY

The number of patients who enroll, discontinue, or complete the study will be summarized. Reasons for premature study treatment discontinuation and study discontinuation will be listed and summarized. Enrollment and major protocol deviations will be listed and evaluated for their potential effects on the interpretation of study results.

6.3 SUMMARIES OF DEMOGRAPHIC AND BASELINE CHARACTERISTICS

Demographic and baseline characteristics (including age, sex, race) will be summarized using means, standard deviations, medians, and ranges for continuous variables and proportions for categorical variables, as appropriate.

6.4 SAFETY ANALYSES

The safety analysis population will consist of all patients who received at least one dose of GDC-8264, with patients grouped according to treatment received.

Safety will be assessed through descriptive summaries of exposure to study treatment (such as treatment duration, total dose received, and dose modifications), adverse events, changes in laboratory test results, and changes in ECGs and vital signs. All adverse event data will be listed by patient number.

All verbatim adverse event terms will be mapped to Medical Dictionary for Regulatory Activities thesaurus terms, and adverse event severity will be graded according to the NCI CTCAE v5.0. In addition, infection adverse event severity will be graded according to the BMT CTN Severity Grading Table (see Appendix 7). All adverse events, serious adverse events, adverse events leading to death, adverse events of special interest, and adverse events leading to study treatment discontinuation that occur on or after the first dose of study treatment (i.e., treatment-emergent adverse events) will be summarized by mapped term, appropriate thesaurus level, and severity grade. For events of varying

GDC-8264—Genentech, Inc. 91/Protocol GA43861, Version 4 severity, the highest grade will be used in the summaries. Deaths and cause of death will be summarized.

Relevant laboratory, vital sign (pulse rate, respiratory rate, blood pressure, and temperature), and ECG data will be displayed by time, with grades identified where appropriate. Additionally, a shift table of selected laboratory tests will be used to summarize the baseline and maximum postbaseline severity grade. Changes in vital signs and ECGs will be summarized.

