2. OBJECTIVES AND ENDPOINTS

This study will evaluate the safety, pharmacokinetics, and efficacy of GDC-8264 given in combination with standard-of-care corticosteroid treatment in patients with high-risk aGVHD. The overall purpose of the study is to identify an optimal dose for GDC-8264 for future studies, using all available safety, PK, and efficacy data. Specific objectives and corresponding endpoints for the study are outlined below.

In this protocol, "study drug" refers to GDC-8264; "study treatment" refers to the combination of treatments assigned to patients as part of this study (i.e., GDC-8264 and corticosteroids).

GDC-8264—Genentech, Inc. 32/Protocol GA43861, Version 4

Co-Primary Objectives	Corresponding Endpoint
 To evaluate the safety of GDC-8264 	 Incidence and severity of adverse events, with severity determined according to the NCI CTCAE v5.0 grading scale
To characterize the pharmacokinetics of GDC-8264	 Plasma concentration of GDC-8264 at specified timepoints, and relevant PK parameters
Secondary Objectives	Corresponding Endpoints
 To evaluate the efficacy of GDC-8264 	 ORR, defined as the proportion of patients with a CR, VGPR, or PR on Day 29 with no intervening additional line of aGVHD therapy, as determined by the investigator ^a
	 DOR, defined as the time from response (CR, VGPR or PR) on Day 29 to aGVHD progression from nadir in any organ, new systemic therapy for aGVHD, or death from any cause (whichever occurs first), as determined by the investigator ^a
	Cumulative incidence of aGVHD flares by Day 56
	 Cumulative incidence of NRM by Day 180

Table 1 Objectives and Corresponding Endpoints

aGVHD=acute graft-versus-host disease; BMT CTN=Blood and Marrow Transplant Clinical Trials Network; CR=complete response; DOR=duration of response; FFS=failure-free survival; MAP=Mount Sinai Acute GVHD International Consortium [MAGIC] algorithm probability; NCI CTCAE=National Cancer Institute Common Terminology Criteria for Adverse Events v5.0; NRM=non-relapse mortality; ORR=overall response rate; OS=overall survival; PK=pharmacokinetic; PR=partial response; VGPR=very good partial response.

- ^a Responses are determined by the investigator. See Section 3.1.4 for key definitions and details on response criteria.
- ^b Baseline defined as last value prior to initiation of GDC-8264.

Exploratory Objectives	Corresponding Endpoints

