4.1.1 Inclusion Criteria

Patients must meet the following criteria for study entry:

- Signed Informed Consent Form from the patient or legal representative
- Age ≥18 years at time of signing Informed Consent Form
- Ability to comply with the study protocol, in the investigator's judgment

GDC-8264—Genentech, Inc. 46/Protocol GA43861, Version 4

- Diagnosis of post–allogeneic HSCT aGVHD at screening, with the following aspects of HSCT permissible:
 - Any malignant or non-malignant indication leading to HSCT
 - Any HSCT donor type (e.g., related, unrelated) or stem cell source (i.e., bone marrow, peripheral blood, cord blood)
 - Any GVHD prophylaxis regimen
 - Any conditioning regimen (i.e., myeloablative, reduced intensity, and non-myeloablative)
- Evidence of engraftment post-transplant, as indicated by the following values: ANC $\ge 500/\mu L (0.5 \times 10^9/L)$ and platelet count $\ge 10,000/\mu L (100 \times 10^9/L)$

ANC and platelet counts may be repeated once during screening.

Use of growth-factor supplementation to maintain neutrophil count is allowed.

If platelet-transfusion refractoriness is suspected, platelet count will be measured approximately 1 hour after transfusion.

- Diagnosis of high-risk aGVHD, defined as meeting any one criterion from either of the following sets of refined Minnesota high-risk aGVHD criteria during screening, with staging determined through use of MAGIC aGVHD Target Organ Staging: (see Appendix 4)
 - Single-organ involvement

Stage 4 skin

Stage 3-4 lower GI

Stage 1-4 liver

– Multiple-organ involvement

Stage 1–2 lower GI plus any liver

Stage 2 lower GI plus any skin

Stage 3-4 lower GI plus any liver or skin

Any three-organ involvement

 Initiation of treatment with systemic corticosteroids for aGVHD at a dose of prednisone ≥2 mg/kg/day PO or methylprednisolone ≥2 mg/kg/day intravenously (or equivalent) in divided doses at diagnosis and up to 3 days prior to or on the same day as initiation of GDC-8264 (Day 1), with no taper planned prior to Day 3

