As clinically indicated, corticosteroid treatment may be initiated at a lower dose and increased on Day 1 to the doses specified above. In exceptional cases of administrative delays or other logistical reasons (i.e., due to the potential participant's health insurance provider[s] issues, screening of a patient during weekends, or extended holidays), a participant who has received systemic corticosteroids up to prior to initiation of GDC-8264 (Day 1), may be enrolled, provided that the participant is not experiencing worsening of aGVHD. The MAGIC Principal Investigator and Medical Monitor are available to advise as needed. The investigator will maintain a record of reasons for the delay in enrollment.

• For women of childbearing potential: agreement to remain abstinent (refrain from heterosexual intercourse) or use contraception, as defined below:

Women must remain abstinent or use contraceptive methods with a failure rate of <1% per year during the treatment period and for after the final dose of GDC-8264.

A woman is considered to be of childbearing potential if she is postmenarchal, has not reached a postmenopausal state (≥12 continuous months of amenorrhea with no identified cause other than menopause), and is not permanently infertile due to surgery (i.e., removal of ovaries, fallopian tubes, and/or uterus) or another cause as determined by the investigator (e.g., Müllerian agenesis). Per this definition, a woman with a tubal ligation is considered to be of childbearing potential. The definition of childbearing potential may be adapted for alignment with local guidelines or regulations.

Examples of contraceptive methods with a failure rate of <1% per year include bilateral tubal ligation, male sterilization, hormonal contraceptives that inhibit ovulation, hormone-releasing intrauterine devices, and copper intrauterine devices.

Hormonal contraceptive methods must be supplemented by a barrier method.

The reliability of sexual abstinence should be evaluated in relation to the duration of the clinical trial and the preferred and usual lifestyle of the patient. Periodic abstinence (e.g., calendar, ovulation, symptothermal, or postovulation methods) and withdrawal are not adequate methods of contraception. If required per local guidelines or regulations, locally recognized adequate methods of contraception and information about the reliability of abstinence will be described in the local Informed Consent Form.

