4.1.2 Exclusion Criteria

Patients who meet any of the following criteria will be excluded from study entry:

- Evidence of relapsed, progressing, or persistent malignancy, or treatment for relapse after transplant, or requirement for rapid immune suppression withdrawal as preemergent treatment of early malignancy relapse
- Prior receipt of more than one allogeneic HSCT
- Prior receipt of solid organ transplantation that are target organs for aGVHD (e.g., liver transplant)
- Prior systemic treatment for aGVHD, except for the standard-of-care corticosteroid treatment initiated as part of this trial (see Section 4.3.2.2)

Topical skin corticosteroid treatment and non-absorbable oral corticosteroid treatment for GI aGVHD are permissible.

- Diagnosis of chronic GVHD or overlap syndrome
- Uncontrolled active infection (i.e., progressive symptoms related to infection despite treatment, or persistently positive blood cultures despite treatment, or any other evidence of severe sepsis)

Persistent fever without signs or symptoms will not be interpreted as an uncontrolled active infection.

In the setting of a pandemic or epidemic, screening for active infections should be considered according to local or institutional guidelines or guidelines of applicable professional societies (e.g., American Society of Clinical Oncology [ASCO] or European Society for Medical Oncology [ESMO]).

- Severe organ dysfunction (e.g., acute liver failure, renal failure requiring dialysis, ventilator support, or vasopressor therapy)
- Direct bilirubin >2 mg/dL within 3 days prior to initiation of GDC-8264 unless the elevation is due to Gilbert syndrome or aGVHD
- ALT/SGPT and AST/SGOT > 5 × the upper limit of normal (ULN) within prior to initiation of GDC-8264, unless due to aGVHD

GDC-8264—Genentech, Inc. 49/Protocol GA43861, Version 4

- Creatinine clearance or estimated glomerular filtration rate < 30 mL/min as calculated by institutional practice (e.g., Cockcroft-Gault equation, CKD-EPI equation)
- Treatment with an investigational small molecule therapy within drug elimination half-lives, whichever is longer, prior to initiation of GDC-8264

An investigational therapy is defined as a drug that has not been approved or authorized by the U.S. Food and Drug Administration for any use.

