4.5.3 Physical Examinations

A complete physical examination, performed at screening and other specified visits, should include an evaluation of the head, eyes, ears, nose, and throat, and the cardiovascular, dermatologic, musculoskeletal, respiratory, gastrointestinal, and neurologic systems; genitourinary examinations may be performed if clinically indicated.

The targeted neurologic examination will be focused on motor abnormalities and may include an assessment of orientation, facial and eye movement assessment (e.g., through evaluation of cranial nerves III–VII, XI, XII), and a check for postural tremor or myoclonic movements in the outstretched arm(s). The same assessment performed at baseline should be repeated at each timepoint indicated in Appendix 1.

Limited, symptom-directed physical examinations should be performed at specified visits and as clinically indicated. Changes from abnormalities identified at screening should be recorded in patient notes.

Any abnormality identified at screening or prior to initiation of study drug should be recorded on the appropriate eCRF (unless considered related to a protocol-mandated intervention; see Section 5.3.1). After initiation of study drug, any new or worsened clinically significant abnormalities should be recorded as adverse events on the adverse event eCRF.

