5.3.1 Adverse Event Reporting Period

Investigators will seek information on adverse events at each patient contact. All adverse events, whether reported by the patient or noted by study personnel, will be recorded in the patient's medical record and on the adverse event eCRF.

After informed consent has been obtained but prior to initiation of GDC-8264, *all* serious adverse events should be reported (see Section 5.4.2 for instructions for reporting serious adverse events).

After initiation of GDC-8264, all adverse events will be reported until after the final dose of GDC-8264.

Instructions for reporting adverse events that occur after the adverse event reporting period are provided in Section 5.6.

GDC-8264—Genentech, Inc. 77/Protocol GA43861, Version 4

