5.4.2.1 Events That Occur prior to GDC-8264 Initiation

After informed consent has been obtained but prior to initiation of GDC-8264, *all* serious adverse events should be reported. The paper Clinical Trial Adverse Event/Special Situations Form provided to investigators should be completed and submitted to the Sponsor or its designee immediately (i.e., no more than 24 hours after learning of the event), either by faxing or by scanning and emailing the form using the fax number or email address provided to investigators.

Significant non-serious events or conditions that occur after informed consent, but prior to initiation of GDC-8264, should be reported as medical history.

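### Section 6.4 starts treatment-emergent events at the first dose of a defined term that includes corticosteroids; it should name GDC-8264, and one adverse event table by dose over a common window would be a cheap addition

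*Combined protocol and SAP*

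**What the plan says.** Section 6.4 (Safety Analyses) starts the summaries with events "that occur on or after the first dose of study treatment (i.e., treatment-emergent adverse events) will be summarized by mapped term". Section 2 keeps *study drug* for GDC-8264 alone and says that *study treatment* "refers to the combination of treatments assigned to patients as part of this study (i.e., GDC-8264 and corticosteroids".

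The two components need not start together. Section 4.1.1 allows corticosteroids "in divided doses at diagnosis and up to 3 days prior to or on the same day as initiation of GDC-8264 (Day 1", and "In exceptional cases of administrative delays or other logistical reasons" allows a longer lead-in whose length is blacked out. Section 4.1.2 bars earlier systemic treatment for aGVHD "except for the standard-of-care corticosteroid treatment initiated as part of this trial", which treats that corticosteroid course as belonging to the trial.

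Capture before GDC-8264 depends on seriousness. Between consent and the first GDC-8264 dose, Section 5.3.1 says that all "serious adverse events should be reported (see Section 5.4.2 for instructions for reporting serious adverse events". For the same interval, Section 5.4.2.1 says: "Significant non-serious events or conditions that occur after informed consent, but prior to initiation of GDC-8264, should be reported as medical history".

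After GDC-8264 starts, all adverse events are reported until a blacked-out time after its final dose (Section 5.3.1). Treatment lasts 28 days. Patients in response on Day 29 may have 28 more at the investigator's discretion (Sections 3.1.1 and 4.3.2.1). Section 6.4 describes no event table over a common window. Section 6 leaves detailed methods to the DAP, which is not among the documents.

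**The concern.** The protocol defines two terms, and Section 6.4 uses the wider one for its starting point. A programmer who applies the definition would count serious events that happened before the patient took any GDC-8264. In that interval only serious events are captured as adverse events, so the tables would join a serious-only period to an all-events period. The safety population is defined by having received GDC-8264, so events and population would have different starting points. Incidence and severity of adverse events is a co-primary endpoint, and there is no corticosteroid-only arm, so the absolute incidence is itself a reported result.

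A lesser question is the end of the window. Because reporting is tied to the final dose, it is longer for patients who extend. Extension depends on Day 29 response and open-label discretion, so randomization does not balance it. Crude incidence by dose could then differ because one cohort was observed for longer.

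**Working it through.** **Plan's own figures.** 28 + 28 = 56 days of treatment with extension, as Section 4.3.2.1 states. With a post-dose reporting period of *x* days (blacked out), the window is 28 + *x* or 56 + *x* days, a difference of 28 for any *x* among patients who complete their period. About 20 per cohort × 2 = 40. There is no power calculation to reproduce.

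**Part 1: serious events before GDC-8264**

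Only days after both consent and the first corticosteroid dose count. If either falls on Day 1, the effect is zero.

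Assumptions, none given in the documents: 28-day serious-event incidence *I* of 10% to 60%; *d* = 1 to 3 days of overlap; share *f* of patients with any overlap; constant hazard, carried back before dosing.

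- Daily hazard: h = −ln(1 − I)/28.
- Added incidence: f × {[1 − exp(−h(28 + d))] − I}.

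In percentage points, with *f* = 1:

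| I | d = 1 | d = 3 |
|---|---|---|
| 10% | 0.34 | 1.01 |
| 30% | 0.89 | 2.62 |
| 60% | 1.29 | 3.74 |

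- *f* = 1: 0.14 to 1.50 patients of 40.
- *f* = 0.5: 0.17 to 1.87 points, or 0.07 to 0.75 patients.
- *f* = 0.25: 0.08 to 0.94 points, or 0.03 to 0.37 patients.

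These are patients added to the any-serious-event count. Patients with some pre-drug serious event are more numerous, because part of them would have a later one anyway. With a full 3-day overlap in all 40, 40 × [1 − exp(−3h)] gives 0.2 at 0.0015/day (the 12-month severe-infection rate of 42.9% in Section 1.1: −ln(1 − 0.429)/365) and 2.3 at an assumed 0.02/day.

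**Part 2: unequal reporting windows**

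Illustration: Section 1.1 cites 64.7% with any infection through Day 56 in an earlier trial, so h = −ln(1 − 0.647)/56 = 0.01859/day. The same hazard is used in both cohorts, so any difference is artefact.

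- *x* = 14: risk 54.2% at 42 days and 72.8% at 70 days.
- *x* = 30: risk 66.0% at 58 days and 79.8% at 86 days.

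Cohort incidence = e × (risk extended) + (1 − e) × (risk not extended), with extension share *e* assumed:

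| Shares extending | x = 14 | x = 30 |
|---|---|---|
| equal | 0 | 0 |
| 60% v 50% | 1.9 points | 1.4 points |
| 70% v 40% | 67.2 − 61.6 = 5.6 points (SE 15.1) | 75.7 − 71.5 = 4.1 points (SE 13.9) |

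SE = √[p₁(1 − p₁)/20 + p₂(1 − p₂)/20].

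If responders have half the hazard and all of them extend, 70% v 40% gives −1.9 points (*x* = 14) or −3.3 (*x* = 30), so the sign can reverse. If the primary-analysis data stop at or before Day 28 + *x* (Day 42 or Day 58 here), the artefact is zero.

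**Check of a Day 1–29 table.** Extension contributes nothing, whatever the shape of the hazard. If *x* is at least 28, reporting reaches Day 29 in all survivors. At *x* = 14, patients whose last dose is before Day 15 are cut short: 20% v 10% stopping at Day 7 gives 0.10 × (41.7% − 32.3%) = 0.9 points.

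**The case against.** On part 1, a reader might infer that the plan will count pre-drug serious events and so report a wrong incidence. The documents do not support that.

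- Section 6.4 defines the safety population by GDC-8264, and Sections 5.3.1 and 4.5.3 tie event recording to it; the latter says "After initiation of study drug, any new or worsened clinically significant abnormalities should be recorded as adverse events on the adverse event eCRF".
- The protocol uses *study treatment* loosely elsewhere. Section 5.4.2.2 ends serious-event reporting by the final GDC-8264 dose, then calls later events those after the final dose of study treatment and points to Section 5.6, which again uses GDC-8264. In Table 7 the QTcF baseline precedes study treatment, whereas Table 1 sets baseline before GDC-8264.
- The literal reading can be disputed. Section 2 limits the term to treatments assigned in the study; assignment follows consent and eligibility (Section 4.2.1), and corticosteroids are site-supplied standard of care. Section 4.1.2 points the other way.
- For pre-drug serious events, Section 5.4.2.1 names only a paper form, so it is not settled that they reach the analysis dataset.
- The hazard before dosing may be lower than assumed: some patients with such an event may never be dosed, and worsening aGVHD is not an adverse event (Section 5.3.5.9).

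All of this stands. It lowers the likelihood and size of a miscount, but the definition still says something other than what is probably meant.

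On part 2, the objection is that the DAP may already provide the table, that the data cut and post-dose period are blacked out, and that Section 6.4 already plans summaries of treatment duration and a by-patient listing. This also stands. Those outputs show unequal exposure but do not give incidence over equal time, so the table is still useful if nothing else supplies it.

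**Conclusion.** Part 1 is a wording error in a co-primary safety definition, with consequences only if the defined term is applied literally. In that case the main scenario (half of patients with 1 to 3 days of overlap) adds under one patient in 40 to serious-event incidence; full overlap adds at most 1.5. The incidence, overlap and constant hazard behind these figures are assumed.

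A reader might go on to infer bias between the doses. None is expected: the corticosteroid lead-in precedes GDC-8264 and the same rules apply to both cohorts. Investigator causality is also untouched, since Section 5.3.4 weighs timing against the start of GDC-8264.

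Part 2 is an improvement, not an error. A reader might infer that the dose comparison of adverse events is distorted. The documents do not establish this: the effect is zero with equal extension shares or an early enough data cut, its direction is not fixed, and the illustrated 1.4 to 5.6 points are well below a standard error of 14 to 15 points at 20 per cohort.

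**What to change.** 1. In Section 6.4, start treatment-emergent events at the first dose of GDC-8264 instead of study treatment. In the by-patient event listing already planned, flag serious events with onset before GDC-8264. Cost: one phrase and one flag.

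2. Keep the crude tables. Unless the DAP or the primary-analysis data period already provides it, add one adverse event table by dose restricted to Day 1–29, stating how many patients' event reporting ended before Day 29. Cost: at most one extra table, with no new data collection.

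Exposure-adjusted rates are optional. They need a footnote that they remove the follow-up artefact only under a constant hazard: with identical hazards in both doses that fall after Day 28 to a half or a quarter, and 70% v 40% extending, the rate ratio is 0.93 to 0.97 instead of 1.00.
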